- 70 - To assess the increase in diagnostic accuracy of adding advanced neuroimaging
71 modalities to standard MRI for the detection of diffuse glioma infiltration within
72 the brain
- 73 - To correlate the information obtained by standard and advanced imaging to
74 histologic and molecular characteristics of the tissue.

75 We hypothesize that advanced neuroimaging, in combination with standard MRI, will
76 have a superior diagnostic accuracy in comparison with standard MRI alone. Besides, we
77 hypothesize that histological and molecular characteristics of (different areas of) glioma
78 will correlate better with advanced imaging than with standard imaging.

79

80 **Study Design**

81 The study design is a monocenter, prospective, diagnostic observational study.

82

83 **Methodology**

84 Subjects

85 *Inclusion criteria*

86 Patients of 18 years and older with a MRI interpretation of a diffuse glioma by an
87 experienced neuroradiologist, and who have an indication for resective surgery; the
88 indication confirmed by the multidisciplinary neuro-oncology tumor board.

89

90 *Exclusion criteria*

91 Patients who are pregnant or have undergone previous brain surgery, cranial irradiation
92 or chemotherapy. Patients with other brain pathology on MRI, such as stroke or multiple
93 sclerosis. Patients with a tumor located infratentorially or in the spinal cord.

94

95 *Withdrawal criteria*

96 Patients who do not successfully undergo one PET scan. A summary of all criteria is
97 given in table 1.

98

99 Study description

100 The study is separated into two phases (Figure 1). In both phases, standard and
101 advanced imaging will be performed pre-operatively (Table 2). Immediately preceding
102 resective surgery, serial image-guided neuronavigated biopsies in and around the
103 glioma boundaries will be obtained using a stereotactic drilling technique.¹¹ Two
104 samples are collected from each biopsy location, one for assessment of histopathologic
105 characteristics and one for molecular analysis.

106 Phase I is designed to decide on the optimal PET tracer, to simplify PET scanning
107 methodology and to develop a robust MRI protocol for glioma volume estimation. Eight
108 patients will receive a dynamic PET protocol with invasive blood sampling, and image-
109 derived carotid input function for metabolite analysis of
110 [18F-]Fluoroethyl-tyrosine (FET) and [11C-]Choline (CHO) tracers, as well as advanced

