111 MR imaging. The data obtained will be used to establish a simplified PET protocol and to
112 determine which of both PET tracers will be further pursued in the next study phase.
113 To obtain a total sample size of 20 patients with a high-grade glioma (WHO grade III or
114 IV) and 20 with a low-grade glioma (WHO grade II), 20 additional patients will receive
115 single advanced MRI and selected simplified PET imaging in the second phase to
116 complete the data acquisition according to the sample size calculation for the main
117 research question.

118

119 Outcome measures

120 *MRI*

121 MRI will be performed using the Philips Achieva whole-body 3.0T MR-scanner, equipped
122 with the standard head coil. Table 2 shows the different techniques.

123

124 *PET*

125 PET will be performed using the Philips Gemini time-of-flight (TOF) PET-CT scanner or
126 the Philips Ingenuity TOF PET/MRI-scanner. After intravenous administration of 370
127 megabecquerel (MBq) of [¹⁵O]H₂O a 10 min dynamic scan is acquired. This is followed
128 by a 40 min dynamic scan after injection of 200 MBq CHO. With a minimum of 4 hours
129 after injection of CHO the FET scan will be performed the same day using 200 MBq FET
130 and a scan time of 90 minutes. During the scans manual blood samples are withdrawn in
131 order to calibrate the online collected arterial input functions and to derive a fully

132 metabolite-corrected plasma input function.

133

134 Of each biopsy site qualitative (high, normal or low signal) and quantitative parameters
135 will be acquired by an experienced neuroradiologist and a nuclear medicine physician
136 (Table 2).

137

138 *Pathology*

139 Of each biopsy location one sample will be processed for histopathologic analysis and
140 the other sample for molecular analysis. Histopathologic analysis will be performed
141 using hematoxylin-and-eosin (H&E) staining and immunohistochemical markers to
142 assess cellularity, glioma infiltration, proliferation, microvascular changes, and necrosis.
143 Molecular analysis will include assessment of DNA mutations, deletions, amplifications
144 and RNA expression profiling. Two experienced neuropathologists will evaluate
145 independently, and blinded for the imaging results, all biopsies and designate those as:
146 normal brain tissue; diffuse glioma with few, moderate or many tumor cells in a
147 background of pre-existent brain tissue; highly cellular glioma without (apparent)

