183 events (SAEs) will be reported through the web portal ToetsingOnline
184 (<https://www.toetsingonline.nl>) to the accredited Medical Ethical Committee (METC)
185 that approved the protocol. SAEs that result in death or are life threatening are reported
186 expeditiously.

187

188 **Follow-up**

189 All patients will receive standard follow-up, which consists of postoperative clinical
190 admission for as long as needed and an outpatient appointment eight weeks after the
191 procedure. Apart from that, postoperative adjuvant chemo- and/or radiotherapy will be
192 installed according to histopathologic and molecular classification of the tumor, as
193 discussed postoperatively at the neuro-oncology tumor board meetings. All adverse
194 events will be followed until they have abated, or until a stable situation has been
195 reached.

196

197 **Data Management and Statistical Analysis**

198 Data will be collected on electronic CRF (eCRF). The eCRF is only assessable by the

199 principal and the study investigator. The eCRF will be completed on site by an
200 investigator. The principal investigator will review the collected data.
201 The number of biopsies and patients required to compare the area under the curve
202 (AUC) of the receiver operating characteristic (ROC) curves depend on the reference
203 AUC (t1), the minimal relevant AUC from the improved imaging (t2), the ratio of non-
204 tumor and tumor biopsies (ratio), the correlation of imaging within patients (r), the
205 average number of biopsies per patient (s), the correlation of histopathologic
206 quantification between biopsies within patients (rho), the type I error (alpha) and the
207 type II error (beta) ²¹⁻²³. Under the assumptions of t1 0.6, t2 0.8, ratio 0.25, r 0.5, s 6, rho
208 0.2, alpha 0.05 and beta 0.2, 20 patients per glioma target volume subgroup are
209 required. The overall study population then comprises 20 non-enhancing and 20
210 enhancing glioma patients, each stratum providing at least 120 biopsies. For testing the
211 correlation between simplified and full quantitative measurement of input function in
212 dynamic PET scanning a sample size of eight is mostly used in pilot studies. Due to the
213 experience with other trials we will include this number in phase I. In phase II 32
214 patients will be included to obtain the total of 40 patients from our sample size
215 calculation.
216 Continuous variables will be described as a mean with standard deviation if the

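### Phase I compares the simplified with the full PET input function by correlation only, which cannot show that one can replace the other

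*Protocol*

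**What the plan says.** In the Protocol, Methodology, Study description, the first purpose given is: "Phase I is designed to decide on the optimal PET tracer, to simplify PET scanning" methodology. Eight patients have dynamic PET with blood sampling. On the use of the results the same section says: "The data obtained will be used to establish a simplified PET protocol and to" select the tracer. Later patients then have "single advanced MRI and selected simplified PET imaging in the second phase to" complete the sample.

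The section Data Management and Statistical Analysis names the comparison. It is a test of the "correlation between simplified and full quantitative measurement of input function in" dynamic PET. The number of patients rests on custom ("dynamic PET scanning a sample size of eight is mostly used in pilot studies") and on experience with other trials. No measure of bias or agreement is named for this comparison, and no target value of r.

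The main analysis, in the same section, compares AUCs. The legend of Table 2 defines a tumor-to-normal (T/N) ratio and SUV among the imaging parameters. The body of that table is not shown.

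**The concern.** The reference in phase I is a plasma input function corrected for metabolites, obtained from blood samples (Outcome measures, PET). The simplified method is meant to stand in for it. To justify that, one must know whether the simplified value is the same as the full value, or by what factor and offset it differs. Correlation answers another question: whether patients who are high on one measure are also high on the other.

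At stake is whether the basis for the phase II PET measurement can support the use made of it. If the simplified values are off by a factor, the named statistic would not show it. Whether that reaches the main result depends on how the PET values are used afterwards, so that step is checked separately below.

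**Working it through.** **1. The plan's own figure.** The eight patients come without a target correlation, alpha or power. The alpha of 0.05 and beta of 0.2 in the same section belong to the AUC comparison. No formula can therefore reproduce the figure 8.

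**2. What correlation can see.** For any a and any b > 0, corr(x, a + b·y) = corr(x, y). If simplified = 0.7 × full in every patient, then r = 1. In an illustrative set of eight simulated pairs with r = 0.992:

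| Change to the simplified value | r | Mean bias |
|---|---|---|
| none | 0.992 | +0.2% |
| × 1.3 | 0.992 | +30% |
| + 0.3 | 0.992 | +29% |
| 0.2 + 0.7 × value | 0.992 | −11% |

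**3. Precision at n = 8, for both approaches.** These figures assume one pair of values per patient.

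- Correlation, by Fisher z: SE = 1/√(8 − 3) = 0.447, so the half-width on the z scale is 1.96 × 0.447 = 0.877. For r = 0.90, tanh(1.472 ± 0.877) gives 0.53 to 0.98. For r = 0.80, tanh(1.099 ± 0.877) gives 0.22 to 0.96.
- Agreement: with t = 2.365 on 7 df, the half-width for the mean bias is 2.365/√8 = 0.84 SD of the paired differences. For each limit of agreement it is 2.365 × √(1/8 + 1.96²/14) = 1.49 SD.

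Both are imprecise, so sample size does not favor one over the other. The case for agreement rests on step 2 alone.

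**4. Effect on the AUC.** The documents give no spread or error size for the PET values. The following is assumed: 80% tumor biopsies (the protocol's ratio of 0.25), true AUC 0.80, and log-normal values with SD s within each class. The class separation on the log scale is then d = 0.8416 × √2 × s.

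- *Same factor in all patients.* The ranks do not change, and the AUC stays at 0.80.
- *Phase I (8) on the full scale and phase II (32) multiplied by 0.7.* The shares are 0.2 and 0.8. Pairs within the same phase make up 0.2² + 0.8² = 0.68, and each kind of cross-phase pair makes up 0.16. With ln 0.7 = −0.357, AUC = 0.68 × 0.80 + 0.16 × Φ((d − 0.357)/(s√2)) + 0.16 × Φ((d + 0.357)/(s√2)).
  - s = 0.15: 0.544 + 0.16 × (0.200 + 0.994) = 0.74
  - s = 0.30: 0.544 + 0.16 × (0.500 + 0.954) = 0.78
  - s = 0.40: 0.544 + 0.16 × (0.584 + 0.930) = 0.79
- *Error that varies between patients (log SD 0.3) with s = 0.30.* For pairs from different patients, AUC = Φ(0.8416 × 0.30/√(0.30² + 0.30²)) = Φ(0.595) = 0.72. A simulation with 20 patients and 6 biopsies each, which includes pairs from the same patient, gives 0.73.

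For scale, the protocol plans to detect an AUC of 0.8 against 0.6.

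**The case against.** **The undetected error may do no harm.** The main analysis is rank-based. A constant factor leaves the AUC unchanged and cancels in a T/N ratio. Error that varies between patients does harm, but it also lowers r, so correlation is not wholly blind to it. This stands. A reader might infer that a biased simplification damages the primary result, and the documents do not show that.

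**The input function may not enter the phase II values.** SUV and T/N need no plasma input, and the legend of Table 2 names no kinetic parameter. This is not conclusive, because the table body is not shown, but it keeps the consequence conditional.

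**Pooling on two scales is not stated.** The protocol does not say that fully quantified phase I values will be combined with simplified phase II values. The dynamic scans may allow the simplified measure to be derived in phase I as well. This stands, and it is a reason to write that step down.

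**Correlation is not a stated pass mark.** It appears in a sentence on pilot size, without a threshold, and an analysis plan could add bias and limits of agreement. It is true that no pass/fail rule is given, so one cannot say that a biased method would pass one. But the protocol does name a statistic for this comparison and ties the eight patients to it, and that statistic does not fit the use made of the result.

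**Further limits.** That the simplified measure is the image-derived one is a plausible inference, but the protocol does not define it. A reader might also take the wide interval for r as an argument against correlation; agreement estimates at n = 8 are imprecise too. Phase II is 32 patients in the statistics section ("experience with other trials we will include this number in phase I. In phase II 32") but 20 in the Study description ("IV) and 20 with a low-grade glioma (WHO grade II), 20 additional patients will receive"). Only 8 + 32 gives the total of 40. The figures in step 4 use 32, and the main point depends on neither number.

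**Conclusion.** The point holds as one of method. Correlation is the only statistic named for a comparison whose result sets the phase II PET protocol, and it cannot reveal constant or proportional bias. This assumes that the simplified and full methods estimate the same quantity, as the protocol's wording implies.

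No effect on the main AUC comparison is shown from the documents. It is zero for a bias common to all patients. It arises only if phase I and phase II values enter on different scales, if the error varies between patients, or if absolute cut-offs are used. Under the assumed values, mixed scales with a 30% shortfall cost 0.01 to 0.06 of AUC, and a patient-varying error of log SD 0.3 costs about 0.07, against a planned difference of 0.2. The change is worth making because it is cheap and gives phase I the quantity it needs.

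**What to change.** Keep the eight patients, the scans and the blood samples. In Data Management and Statistical Analysis, make agreement the primary phase I comparison:

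- the ratio of the areas under the two input curves in each patient;
- the slope and intercept of simplified on full values, by a method that allows error in both, with intervals;
- the mean bias and limits of agreement, with intervals, for the PET parameter carried into phase II;
- correlation as a supplement only.

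If the simplified measure is in other units, such as SUV, report the regression relation in place of limits of agreement. State which measurement is the simplified one. Derive that same measure in the phase I patients, so that all patients enter the ROC analysis on one scale.

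The cost is protocol wording and a little more analysis. The estimates will be imprecise at this size (mean bias about ±0.84 SD of the paired differences) and should be reported with that uncertainty.

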35 Neurosurgery; [name], MD, PhD, Department of Neurology; [name], MD,
36 PhD, Department of Pathology; [name], PhD, Department of Physics & Medical
37 Technology; [name], MD, PhD, [name], MSc, PhD and [name], MD, PhD,
38 Department of Nuclear Medicine & PET Research.

39

40 **Rationale and background information**

41 Gliomas represent 80-90% of parenchymal brain tumors in adults with an incidence of
42 5.9 per 100.000 person-years: approximately 1000 patients per year in The
43 Netherlands. ¹ Most gliomas show extensive infiltration in the brain parenchyma. These
44 so-called diffuse gliomas universally recur, without exception resulting in death despite
45 standard treatment, which consists of as extensive as possible resection, followed by
46 radiation and chemotherapy.

47 Both resective surgery and adjuvant radiation therapy are based on T1 contrast-
48 enhancement for gadolinium-enhancing gliomas and on T2/ Fluid attenuated inversion
49 recovery (FLAIR) hyperintensity volume outlines for non-enhancing gliomas. This
50 strategy is founded on early and preliminary observations, and has remained unchanged
51 since. ^{2,3} Diffuse gliomas recur locally in the vast majority of patients, even after
52 seemingly radical surgical removal and radiation therapy with 2 cm margins. This, and
53 the fact that glioma infiltration has been demonstrated to extend up to two centimeters
54 beyond standard MRI outlines, underscores that up till now delineation of these
55 neoplasms has been less than optimal. ⁴⁻⁷

56 Several publications provide arguments for underestimation of the spread of diffuse
57 gliomas using standard MRI and potential benefit from advanced MRI and positron
58 emission tomography (PET) imaging. Advanced imaging, such as diffusion-weighted
59 imaging (DWI), perfusion-weighted imaging (PWI), magnetic resonance spectroscopy
60 (MRS) and PET, has been shown to be able to identify tumor in areas of normal standard
61 MRI signal. ⁸⁻¹⁰

62 Our study addresses a clinically relevant research question, which so far has not been
63 adequately answered: What is the best neuroimaging approach to discriminate areas
64 with glioma infiltration from brain tissue without glioma cells?

65

66 **Study Goals and Objectives**

67 The goal of this study is thus to determine the best neuroimaging approach for glioma
68 delineation.

69 The specific objectives are:

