217 distribution is symmetric and as a median with minimum and maximum if it is skewed.
218 Categorical variables are presented as numbers with percentages. Data analysis will be
219 performed using R. AUCs are compared using a nonparametric resampling test using
220 pROC in R. ²⁴⁻²⁶ Next, multivariate logistic regression analysis modeling histopathology
221 by quantitative imaging is performed using Bayesian models.

222

223 **Quality Assurance**

224 As the METC of VU University Medical Center (VUmc) decided it was unnecessary to
225 appoint a Data Safety Monitoring Board for this study, the progress of this study will be
226 monitored by the Clinical Research Bureau of VUmc.

227

228 **Expected Outcomes of the Study**

229 We expect that advanced imaging in combination with standard imaging, will have a
230 superior diagnostic accuracy for glioma delineation compared with current standard
231 imaging. This delineation could help neurosurgeons, neurologists, radiation oncologists

232 and medical oncologists in their clinical decision-making. Next, studies comparing
233 glioma resection or radiotherapy using standard versus standard plus advanced imaging
234 can be conducted to investigate possible influences on clinical outcome.
235 The expected correlation between advanced imaging and histologic and molecular
236 characteristics could provide biomarkers for prognosis and choice of therapy, as well as
237 further insight into glioma imaging

238

239 **Duration of the Project**

240 We anticipate that phase I will take 12 months and phase II 24 months, aiming for a total
241 study duration of three years.

242

243 **Project Management**

244 The principal investigator, [name], will lead the study. [name] will be
245 responsible for the MRS data, [name] for the MRI data, [name] and Dr.
246 [name] for the PET data, and [name] for the pathology data. The study
247 investigator, [name], MSc, will coordinate the logistics and of the study as well as
248 the interpretation of the results.

249

250 **Ethics**

251 The study is approved by the METC of VUmc and will be conducted according to the
252 principles of the Declaration of Helsinki and in accordance with the Medical Research
253 Involving Human Subjects Act. Explicit written consent will be obtained from all patients
254 in this study.

255 **Disclosures**

256 Financial support was provided by grant CCA2012-2-05 of the Cancer Center

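### On its natural reading the AUC comparison sets tumour in one patient against non-tumour tissue in another for about 95-97% of pairs; a within-patient result should stand beside it, because the goal is delineation within the brain

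*Protocol*

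**What the plan says.** The Rationale calls the open question one not yet "adequately answered: What is the best neuroimaging approach to discriminate areas" with infiltration from those without. Study Goals and Objectives states: "The goal of this study is thus to determine the best neuroimaging approach for glioma" delineation. Its first objective is the accuracy gained by adding advanced "modalities to standard MRI for the detection of diffuse glioma infiltration within" the brain.

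Data Management and Statistical Analysis sizes the AUC comparison: "Under the assumptions of t1 0.6, t2 0.8, ratio 0.25, r 0.5, s 6, rho", continuing "0.2, alpha 0.05 and beta 0.2, 20 patients per glioma target volume subgroup are" required. Here rho is the correlation of histopathologic "quantification between biopsies within patients (rho"). The population is 20 non-enhancing and 20 "enhancing glioma patients, each stratum providing at least 120 biopsies".

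The analysis itself reads "AUCs are compared using a nonparametric resampling test using" pROC in R. A multivariate logistic regression of histopathology on quantitative imaging, fitted with Bayesian models, follows. No within-patient, patient-stratified or patient-adjusted AUC is named, and no patient effect is given for the regression.

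**The concern.** Delineation means telling infiltrated from free tissue inside one brain. An AUC is the proportion of tumour/non-tumour pairs that a modality ranks correctly. When biopsies of many patients are pooled, nearly all of those pairs join two different patients. If a modality's general level varies from patient to patient, two things can happen:

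- Offsets unrelated to tumour share blur the pooled ranking and understate a real within-patient gain.
- Offsets that follow a patient's share of tumour biopsies raise the pooled AUC although the modality locates no boundary better.

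The number of biopsies per patient and rho enter the sample size as clustering terms. They correct the variance. They do not change which pairs the AUC compares.

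**Working it through.** **Inputs from the protocol (per stratum).** n = 20 patients, s = 6 biopsies, AUC 0.6 against 0.8, r = 0.5, rho = 0.2, non-tumour to tumour ratio 0.25. So the tumour share is p = 0.8, with 96 tumour and 24 non-tumour biopsies of 120.

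**The plan's own figure.** Use the Hanley-McNeil variance per tumour biopsy, V = (Q1 - A²)/0.25 + (Q2 - A²), with Q1 = A/(2 - A) and Q2 = 2A²/(1 + A).
- V(0.6) = 0.364 and V(0.8) = 0.178.
- Variance of the difference: 0.364 + 0.178 - 2 × 0.5 × √(0.364 × 0.178) = 0.288.
- One-sided alpha 0.05: (1.645 + 0.842)² × 0.288 / 0.2² ≈ 44.5 tumour biopsies.
- Total 44.5 × 1.25 = 55.6. Times the design effect 1 + 5 × 0.2 = 2 gives 111, and divided by 6 gives 18.5 patients.

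The Obuchowski variance gives 21.0, so 20 is reproduced approximately. Two-sided, the literal ratio gives 23.1 to 29.8; sidedness is not stated. The figure is thus recovered by counting biopsies across a stratum, which supports the pooled reading.

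**Share of same-patient pairs (expected).**
- Within patients: n × s(s - 1) × p(1 - p) × (1 - rho) = 20 × 30 × 0.16 × 0.8 = 76.8.
- Between patients: n(n - 1) × s² × p(1 - p) = 380 × 36 × 0.16 = 2188.8.
- Within share: 76.8 / 2265.6 = 3.4%. With rho = 0 it is 96 / 2284.8 = 4.2%, and with a perfectly even split 1/20 = 5%.

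So about 95-97% of pairs compare different patients.

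**Patients with both tissue types.** With rho = 0.2 (beta-binomial), 42.3% have no non-tumour biopsy and 0.7% have only non-tumour biopsies. That leaves 57% of 20, about 11. With independent labels 0.8⁶ = 26% have no non-tumour biopsy, which leaves about 15.

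**Effect of offsets (assumed).** Let k be the ratio of patient-level to within-patient SD. The protocol gives no value; k = 0.5 to 1 is used here.

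*Unrelated offsets, same size in both modalities.* The between-patient AUC is Φ(z/√(1 + k²)), where z = 0.842 for 0.80 and 0.253 for 0.60.

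| k | AUC 0.80 becomes | AUC 0.60 becomes | gain |
|---|---|---|---|
| 0 | 0.800 | 0.600 | 0.20 |
| 0.5 | 0.774 | 0.590 | 0.18 |
| 1 | 0.724 | 0.571 | 0.15 |

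Simulation at k = 1 gave a gain of 0.152, and power fell from 89% to 40%.

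*No true gain (both 0.60), advanced-modality offset correlated 0.5 with tumour share.* The SD of the tumour share is √(0.8 × 0.2 × 0.2) = 0.179. Its standardised mean differs between tumour and non-tumour biopsies by 0.179 × (1/0.8 + 1/0.2) = 1.118. The offset therefore adds k × 0.5 × 1.118 to the separation of √2 × 0.253 = 0.358.
- k = 0.5: Φ((0.358 + 0.280)/√2.5) = 0.657.
- k = 1: Φ((0.358 + 0.559)/2) = 0.677.

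Against a standard modality without offsets (0.600) the false gain is 0.057 or 0.077. Against one with unrelated offsets of the same size (0.590 or 0.571) it is 0.067 or 0.106. These are normal approximations for between-patient pairs. Simulation gave 0.054 and 0.075 in the first case, and 0.654 - 0.590 = 0.064 and 0.668 - 0.573 = 0.095 in the second. A false gain of about 0.06-0.09 summarises them. In the first case the simulated false-positive rates were 16% and 20%, against about 4.5% without offsets.

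**Same-patient pairs only.** In the same simulations the within-patient gain stayed near 0.20 or near 0 whatever the offset. Its power was about 62-66%.

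**The case against.** **The text does not say that biopsies are pooled, and the SAP is not at hand.** This stands as a limit. Supporting AUCs and covariate coding often belong in a SAP, so their absence is not itself an error. What the protocol does fix is the accuracy measure and a biopsy-based sample size, set beside a goal within the brain.

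**Delineation is not purely within-patient.** A new patient has no biopsies for calibration, so a cut-off must carry over from others. Large offsets are then a real weakness, and the pooled AUC is right to penalise them. This stands. A reader might infer that the trial cannot answer its own question; the protocol does not support that. The pooled AUC answers a relevant question, but not the whole one.

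**The offsets are assumed.** This also stands. A false gain needs offsets that track tumour share and differ between modalities; unrelated ones create none. It is tempting to read r = 0.5 as the plan's own admission of imaging offsets. Its definition can equally mean the correlation between modalities, so r is not evidence here. Nor does the protocol say that 0.6 and 0.8 are within-patient AUCs; if they are already on the pooled scale, the planned 0.20 does not shrink.

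**Normalisation.** The Table 2 caption defines a tumour-to-normal ratio, which would reduce offsets for the parameters it covers. The caption also lists SUV, FA, ADC, CBF and CBV. The table body is not available here, so how far normalisation extends cannot be judged.

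**Conclusion.** The point holds as a recommended improvement, not as a demonstrated error. On the pooled reading, 95-97% of tumour/non-tumour pairs are between patients; that follows from the protocol's own figures. The pooled AUC alone therefore cannot show whether a gain is better delineation within patients or a difference between them.

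The size of any distortion is conditional. At an assumed patient to within-patient SD ratio of 0.5 to 1, a true within-patient gain of 0.20 appears as about 0.18-0.15. With an assumed correlation of 0.5 between offset and tumour share in the advanced modality only, a gain of about 0.06-0.09 appears where none exists, which is 30-45% of the planned 0.20. Normalised parameters would show less.

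**What to change.** Keep the pooled AUC as the powered comparison and add two analyses in each stratum:

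1. Report the within-patient AUC difference, using only tumour/non-tumour pairs of the same patient, with an interval from a bootstrap that resamples patients. Label it a supporting result.
2. In the planned Bayesian logistic model, include a patient intercept and enter each imaging parameter as the patient's mean plus the deviation from it. Report the deviation effect as the evidence on delineation.

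A rule that allows a claim only when the within-patient and pooled differences share a sign is not worth adding. When there was no true within-patient gain, about 71-78% of false-positive pooled results still agreed in sign.

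The cost is analysis wording and reporting; no patients, scans or biopsies are added. The downside is precision. The within-patient AUC rests on about 77 pairs from about 11 patients per stratum (about 96 pairs from about 15 patients if labels are independent). In most settings it is less precise than the pooled AUC: power was about 66% against 89% without offsets, although at k = 1 in both modalities it was 64% against 40%. It should support the pooled test and not replace it. The regression keeps all patients.
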